		AORTIC: FLOW OBSTRUCTION OF THE AORTIC VALVE DUE TO RESTRICTED LEAFLET OPENING. THE SEVERITY IS CATEGORIZED AS: MILD - JET VELOCITY (M/S) <3.0; MEAN GRADIENT (MMHG) <25; VALVE AREA (CM2) >1.5.MODERATE - JET VELOCITY (M/S) 3.0-4.0; MEAN GRADIENT (MMHG) 25-40; VALVE AREA (CM2) 1.0- 1.5. OR SEVERE - JET VELOCITY (M/S) >4.0; MEAN GRADIENT (MMHG) >40; VALVE AREA (CM2) <1.0; VALVE AREA INDEX<0.6. MITRAL: MITRAL STENOSIS (MS) REFERS TO NARROWING OF THE MITRAL VALVE ORIFICE, RESULTING IN IMPEDANCE OF FILLING OF THE LEFT VENTRICLE IN DIASTOLE. THE SEVERITY OF MS IS CATEGORIZED AS: MILD - MEAN GRADIENT (MM HG) < 5, PULMONARY ARTERY SYSTOLIC PRESSURE (MM HG) < 30, VALVE AREA (CM2) >1.5. MODERATE - MEAN GRADIENT (MM HG) 5-10, PULMONARY ARTERY SYSTOLIC PRESSURE (MM HG) 30-50, VALVE AREA (CM2) 1.0-1.5. SEVERE - MEAN GRADIENT (MM HG) > 10, PULMONARY ARTERY SYSTOLIC PRESSURE (MM HG)> 50, VALVE AREA (CM2) <1.0. TRICUSPID: A NARROWING OF THE TRICUSPID VALVE OPENING THAT INCREASES RESISTANCE TO BLOOD FLOW FROM THE RIGHT ATRIUM TO THE RIGHT VENTRICLE. SEVERE TRICUSPID STENOSIS IS DEFINED AS A VALVE AREA LESS THAN 1.0 CM2.
AE220*	STENOSIS - AORTIC - MILD	"
AE221*	STENOSIS - AORTIC - MODERATE	"
AE222*	STENOSIS - AORTIC - SEVERE	"
AE223	STENOSIS - MITRAL- MILD	"
AE224	STENOSIS - MITRAL - MODERATE	"
AE225	STENOSIS - MITRAL - SEVERE	"
AE226	STENOSIS - PULMONARY- MILD	"
AE227	STENOSIS - PULMONARY - MODERATE	"
AE228	STENOSIS - PULMONARY - SEVERE	"
AE229	STENOSIS - TRICUSPID- MILD	"
AE230	STENOSIS - TRICUSPID- MODERATE	"
AE231	STENOSIS - TRICUSPID - SEVERE	"

AE CODE LIST	
CODE	DEFINITION
AE.6	
CARDIOVASCULAR - THROMBOEMBOLIC EVENT/VALVE THROMBOSIS
 
ANY EMBOLIC EVENT THAT OCCURS IN THE ABSENCE OF INFECTION AFTER THE IMMEDIATE PERIOPERATIVE PERIOD AND MAY BE MANIFESTED BY A NEUROLOGIC EVENT OR A NON-CEREBRAL EMBOLIC EVENT. EMBOLI CONSISTING OF NON-THROMBOTIC MATERIAL (E.G., ATHEROSCLEROSIS, MYXOMA) ARE NOT COUNTED.

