AE250	
THROMBOEMBOLIC EVENT – STROKE
 
INCLUDES ANY CENTRAL, NEW NEUROLOGIC DEFICIT, WHETHER TEMPORARY OR PERMANENT AND WHETHER FOCAL OR GLOBAL, THAT OCCURS AFTER THE SUBJECT EMERGES FROM ANESTHESIA. POSTOPERATIVE NEUROLOGIC SYMPTOMS THAT MIMIC THOSE OF A PREOPERATIVELY DOCUMENTED NEUROLOGIC EVENT AND THAT ARE CONFIRMED RADIOGRAPHICALLY TO BE CONSISTENT WITH THE FORMER EVENT ARE NOT COUNTED. CENTRAL NEUROLOGIC EVENTS THAT ARE CLEARLY RELATED TO AORTIC, INTERNAL CAROTID ARTERY, OR VERTEBRAL ARTERY DISEASE ARE ALSO NOT COUNTED. PSYCHOMOTOR DEFICITS FOUND BY SPECIALIZED TESTING ARE NOT CONSIDERED NEUROLOGIC EVENTS RELATED TO OPERATED VALVES. SUBJECTS WHO DO NOT AWAKEN OR WHO AWAKEN AFTER OPERATION WITH A NEW STROKE ARE NOT CONSIDERED TO HAVE SUSTAINED VALVE-RELATED NEUROLOGIC EVENTS. STROKE: A PROLONGED (>72 HOURS) OR PERMANENT NEUROLOGIC DEFICIT THAT IS USUALLY ASSOCIATED WITH ABNORMAL RESULTS OF MRI OR CT SCANS. SUBJECTS WITH MINIMAL, ATYPICAL, OR PROTEAN SYMPTOMS THAT LEAD TO RADIOGRAPHIC IMAGING DEMONSTRATING AN ACUTE ISCHEMIC EVENT ARE CONSIDERED TO HAVE SUSTAINED A STROKE. TIA: CHARACTERIZED BY FULLY REVERSIBLE SYMPTOMS OF SHORT DURATION. IF RADIOGRAPHIC IMAGING DEMONSTRATES AN ACUTE CENTRAL NEUROLOGIC LESION, HOWEVER, SUCH SUBJECTS ARE RECLASSIFIED AS HAVING SUSTAINED A STROKE.

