AE262	VALVE THROMBOSIS - AORTIC ANY THROMBUS NOT CAUSED BY INFECTION ATTACHED TO OR NEAR AN OPERATED VALVE THAT OCCLUDES PART OF THE BLOOD FLOW PATH, INTERFERES WITH VALVE FUNCTION, OR IS SUFFICIENTLY LARGE TO WARRANT TREATMENT. VALVE THROMBUS FOUND AT AUTOPSY IN A SUBJECT WHOSE CAUSE OF DEATH WAS NOT VALVE RELATED OR FOUND AT OPERATION FOR AN UNRELATED INDICATION SHOULD ALSO BE COUNTED.
AE263	VALVE THROMBOSIS - MITRAL "
AE264	VALVE THROMBOSIS - PULMONARY "
AE265	VALVE THROMBOSIS - TRICUSPID "
AE.7	CARDIOVASCULAR - MISC
AE270	ANGINA, STABLE CHEST PAIN, TIGHT OR HEAVY FEELING IN THE CHEST, OR DISCOMFORT WHICH SPREADS FROM THE CHEST TO THE ARM, BACK, NECK, JAW, OR STOMACH, NUMBNESS OR TINGLING IN THE SHOULDERS, ARMS OR WRISTS, SHORTNESS OF BREATH, AND NAUSEA RELIEVED BY REST OR NITROGLYCERINE AND/OR CONFIRMED BY ECG. STABLE ANGINA IS ANGINA THAT IS CONTROLLED BY ORAL AND/OR TRANSCUTANEOUS MEDICATION.
AE271	ANGINA, UNSTABLE UNSTABLE ANGINA IS ANGINA, WHICH NECESSITATES THE INITIATION, CONTINUATION OR INCREASE OF ANGINA CONTROL THERAPIES THAT MAY INCLUDE: NITROGLYCERIN DRIP, HEPARIN DRIP, OR IABP PLACEMENT. THE TYPE OF ANGINA MAY INCLUDE, BUT IS NOT LIMITED TO: REST ANGINA, NEW ONSET EXERTIONAL ANGINA OF AT LEAST NEW YORK HEART ASSOCIATION (NYHA) CLASS III IN SEVERITY, RECENT ACCELERATION IN PATTERN AND INCREASE OF ONE NYHA CLASS TO AT LEAST NYHA CLASS III, VARIANT ANGINA, NON-Q WAVE MYOCARDIAL INFARCTION, OR POST-INFARCTION ANGINA.
AE272	ANNULAR DISSECTION DISSECTION OF THE VALVULAR ANNULUS EXTENDING INTO THE AORTA. ANNULAR DISSECTION OCCURRING WITHIN 30 DAYS OF THE INDEX PROCEDURE WILL BE CONSIDERED VALVE RELATED. SHOULD BE CONFIRMED BY IMAGING, OR DIRECT VISUAL INSPECTION.
AE273	AORTIC DISSECTION DISRUPTION OF THE MEDIA LAYER OF THE AORTA WITH BLEEDING WITHIN AND ALONG THE WALL OF THE AORTA. AORTIC DISSECTION MAY OCCUR IN THE ASCENDING THORACIC AORTA (TYPE A DISSECTION) OR IN THE DESCENDING THORACIC AORTA (TYPE B DISSECTION). DISSECTION SHOULD BE CONFIRMED BY IMAGING OR DIRECT VISUAL INSPECTION.
AE274	ARTERIAL DISSECTION DISRUPTION OF THE MEDIA LAYER OF AN ARTERY OTHER THAN THE AORTA WITH BLEEDING WITHIN AND ALONG THE WALL OF THE VESSEL. SHOULD BE CONFIRMED BY IMAGING OR DIRECT VISUAL INSPECTION.
AE275	CARDIAC ARREST CARDIAC ARREST DOCUMENTED BY ONE OF THE FOLLOWING: VENTRICULAR FIBRILLATION, RAPID VENTRICULAR TACHYCARDIA WITH HEMODYNAMIC INSTABILITY, ASYSTOLE.

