AE276	CARDIAC DECOMPENSATION AN INABILITY OF THE HEART TO MAINTAIN ADEQUATE CIRCULATION; IT IS MARKED BY DYSPNEA, VENOUS ENGORGEMENT, CYANOSIS AND EDEMA.

Clinical Investigational Plan
Protocol Number: 2010-03

AE CODE LIST	
CODE	DEFINITION
AE277	CARDIOGENIC SHOCK A CLINICAL STATE OF HYPOPERFUSION SUSTAINED FOR GREATER THAN 30 MINUTES, WITH EITHER SYSTOLIC BLOOD PRESSURE < 80 MM HG, AND /OR CARDIAC INDEX < 1.8 DESPITE MAXIMAL TREATMENT (FLUIDS) OR REQUIRING INTRAVENOUS INOTROPES AND/OR PRESSOR AGENT OR AN INTRA-AORTIC BALLOON PUMP (IABP).
AE.7	CARDIOVASCULAR - MISC (CONTINUED)
AE278	CHORDAE TENDINEAE DAMAGE
AE279	CORONARY ARTERY OSTIAL OBSTRUCTION OBSTRUCTION OF THE CORONARY OSTIA. SHOULD BE CONFIRMED BY IMAGING AND THE SOURCE OF THE OBSTRUCTION (AORTIC VALVE, THROMBUS, ETC. SHOULD BE REPORTED.
AE280	ENDOCARDITIS ANY INFECTION INVOLVING THE STUDY VALVE. THE DIAGNOSIS OF OPERATED VALVULAR ENDOCARDITIS IS BASED ON ONE OF THE FOLLOWING CRITERIA: (1) REOPERATION WITH EVIDENCE OF ABSCESS, PARAVALVULAR LEAK, PUS, OR VEGETATION CONFIRMED AS SECONDARY TO INFECTION BY HISTOLOGIC OR MICROBIOLOGIC STUDIES; (2) AUTOPSY FINDINGS OF ABSCESS, PUS, OR VEGETATION INVOLVING A REPAIRED OR REPLACED VALVE; OR (3) IN THE ABSENCE OF REOPERATION OR AUTOPSY, MEETING OF THE DUKE CRITERIA FOR ENDOCARDITIS [4]. MORBIDITIES ASSOCIATED WITH ACTIVE INFECTION, SUCH AS VALVE THROMBOSIS, THROMBOTIC EMBOLUS, BLEEDING EVENT, OR PARAVALVULAR LEAK, ARE INCLUDED UNDER THIS CATEGORY, BUT NOT COUNTED IN OTHER CATEGORIES OF MORBIDITY.
AE281	HEART FAILURE – ACUTE ACUTE HEART FAILURE DESCRIBES EXACERBATED OR DECOMPENSATED HEART FAILURE, REFERRING TO EPISODES IN WHICH A SUBJECT IS CHARACTERIZED AS HAVING A CHANGE IN HEART FAILURE SIGNS AND SYMPTOMS RESULTING IN A NEED FOR URGENT THERAPY OR HOSPITALIZATION.
AE282	HEART FAILURE – CHRONIC (CHF) AN EVENT IN WHICH THE HEART FAILS TO MEET THE CIRCULATORY REQUIREMENTS OF THE BODY UNDER DIFFERING PHYSIOLOGICAL CIRCUMSTANCES, AND/OR A STATE IN WHICH CARDIAC OUTPUT IS REDUCED RELATIVE TO THE DEMANDS OF THE BODY, ASSUMING THE EVIDENCE OF ADEQUATE VENOUS RETURN. EVENT IS CONFIRMED CLINICALLY OR BY DIAGNOSTIC TESTING.
AE283	HYPERTENSION – SYSTEMIC DEFINED AS BLOOD PRESSURE > 140 /90 MM HG FOR SUBJECT WITHOUT DIABETES OR KIDNEY DISEASE; >130/80 MMHG FOR SUBJECTS ON 2 OCCASIONS WITH DIABETES OR RENAL DISEASE. UNLESS DUE TO PRESENCE OF MEDICATION, E.G. BETA BLOCKERS FOR 10 YEARS

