
AE CODE LIST	
CODE	DEFINITION

AE CODE LIST	
CODE	DEFINITION
AE.10	PULMONARY/RESPIRATORY
AE394	RESPIRATORY FAILURE -ASTHMA
AE395	RESPIRATORY FAILURE -EMPHYSEMA
AE396	RESPIRATORY FAILURE -COPD
AE397	RESPIRATORY FAILURE -PNEUMONIA
AE398	RESPIRATORY FAILURE -PNEUMOTHORAX
AE399	RESPIRATORY FAILURE -HEMOTHORAX
AE400	RESPIRATORY FAILURE - ARDS
AE401	RESPIRATORY FAILURE -OTHER
AE402	RESPIRATORY INFECTION – UPPER (URI)
AE403	RESPIRATORY INFECTION – PNEUMONIA
AE.11	PERIPHERAL VASCULAR
AE420	VASCULAR - ACCESS SITE COMPLICATION
AE421	VASCULAR - DEEP VEIN THROMBOSIS (DVT)
AE423	VASCULAR - OTHER
AE.12	PSYCHIATRIC
AE431	PSYCHIATRIC DISORDER
AE432	SUICIDE
AE433	TRANSIENT PSYCHOTIC SYNDROME

NEED FOR MECHANICAL VENTILATION REQUIRED GREATER THAN 24 HRS AFTER OF COMPLETION OF THE INDEX PROCEDURE (TIME 0 = WHEN THE SUBJECT LEAVES THE OR), OR NEED FOR RE-INTUBATION AND VENTILATOR SUPPORT OCCURRING ANY TIME WITHIN 30 DAY OF THE INDEX PROCEDURE WILL BE CONSIDERED RELATED TO THE INDEX PROCEDURE.

"

"

"

"

"

" ACUTE RESPIRATORY DISTRESS SYNDROME

"

THE ILLNESSES CAUSED BY AN ACUTE INFECTION WHICH INVOLVES THE UPPER RESPIRATORY TRACT: NOSE, SINUSES, PHARYNX OR LARYNX. THIS COMMONLY INCLUDES: TONSILLITIS, PHARYNGITIS, LARYNGITIS, SINUSITIS, OTITIS MEDIA, AND THE COMMON COLD.

LUNG INFECTION DOCUMENTED BY BLOOD STUDIES OR CHEST X-RAY, REQUIRING TREATMENT WITH ANTIBIOTICS, INHALATION THERAPY, INTUBATION OR SUCTIONING.

COMPLICATIONS OF BLEEDING OR INFECTION AT THE SITE OF CARDIOPULMONARY ACCESS AND OR PERCUTANEOUS CORONARY INTERVENTION OR DIAGNOSTICS THAT REQUIRE HOSPITALIZATION OR MEDICAL INTERVENTION.

FORMATION OF BLOOD CLOT (THROMBUS) IN THE LOWER EXTREMITIES (LEGS) CHARACTERIZED BY SWELLING, REDNESS, CLAUDICATION/PAIN IN AFFECTED LIMB. EVENT SHOULD BE CONFIRMED BY DOPPLER OR DUPLEX US STUDY, AND REQUIRES HOSPITALIZATION OR MEDICAL INTERVENTION TO RESOLVE.

OTHER VASCULAR COMPLICATIONS GENERALLY RELATED TO A DISEASE PROCESS AND NOT TRAUMA THAT REQUIRE HOSPITALIZATION OR MEDICAL INTERVENTION.

A PSYCHOLOGICAL OR BEHAVIORAL PATTERN GENERALLY ASSOCIATED WITH SUBJECTIVE DISTRESS OR DISABILITY THAT OCCURS IN AN INDIVIDUAL, AND WHICH IS NOT A PART OF NORMAL DEVELOPMENT OR CULTURE. SUCH A DISORDER MAY CONSIST OF A COMBINATION OF AFFECTIVE, BEHAVIORAL, COGNITIVE AND PERCEPTUAL COMPONENTS.

A PERSON WHO INTENTIONALLY TAKES HIS OR HER OWN LIFE.

A MENTAL STATE OFTEN DESCRIBED AS INVOLVING A "LOSS OF CONTACT WITH REALITY" THAT LASTS ONLY FOR A

AE CODE LIST	
CODE	DEFINITION

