	SHORT TIME.
AE.12	PSYCHIATRIC (CONTINUED)
AE434	PSYCHIATRIC – OTHER
AE.13	MUSCULAR SKELETAL/ DERMATOLOGIC
AE450	STERNAL WOUND/THORACIC INFECTION
AE451	BONE FRACTURE/BREAK
AE452	WOUND INFECTION – OTHER
AE454	INFECTION/INFLAMMATION - OTHER
AE456	MUSCULAR SKELETAL / DERMATOLOGIC - OTHER
AE.14	NONSPECIFIC, UNKNOWN, OR OTHER BODY SYSTEM
AE470	ANAPHYLACTIC REACTION
AE471	ALLERGIC REACTION – MEDICATION RELATED
AE472	ALLERGIC REACTION – OTHER
AE473	CANCER – PROGRESSION OF UNDERLYING DISEASE
AE474	CANCER – NEWLY DIAGNOSED
AE475	HEARING DISORDER
AE476	MULTI-SYSTEM ORGAN FAILURE
AE477	SPEECH DISORDER
AE479	VISION DISORDER
AE480	FEVER - UNKNOWN ORIGIN

AE CODE LIST	
CODE	DEFINITION
AE481	NONSPECIFIC, UNKNOWN, OR OTHER BODY SYSTEM - OTHER COMPLICATION
AE.15	DEVICE DYSFUNCTION
AE500	SVD - STUDY VALVE WEAR
AE501	SVD - STUDY VALVE FRACTURE
AE502	SVD - STUDY VALVE POPPET ESCAPE
AE503	SVD - STUDY VALVE CALCIFICATION
AE504	SVD - STUDY VALVE LEAFLET TEAR
AE505	SVD - STUDY VALVE STENT CREEP
AE506	SVD - STUDY VALVE SUTURE LINE DISRUPTION
AE507	SVD - STRUCTURAL VALVE DETERIORATION, OTHER
AE525	SVD - ANNULAR FRAME DAMAGE
AE526	SVD - ANNULAR FRAME SEPARATION
AE527	SVD - STENT FRAME FRACTURE
AE528	SVD - STENT FRAME DEFORMATION
AE529	SVD - STENT FRAME SEPARATION
AE512	NSD - ENTRAPMENT BY PANNUS, TISSUE, OR SUTURE
AE164	NSD - PARAVALVULAR LEAK - +1
AE165	NSD - PARAVALVULAR LEAK - +2
AE166	NSD - PARAVALVULAR LEAK - +3
AE167	NSD - PARAVALVULAR LEAK - +4
AE176	NSD - STUDY VALVE STENOSIS - MILD

ANY COMPLICATION THAT CANNOT OTHERWISE BE CATEGORIZED REQUIRING HOSPITALIZATION OR MEDICAL INTERVENTION.

INCLUDES DYSFUNCTION OR DETERIORATION INVOLVING THE OPERATED VALVE (EXCLUSIVE OF INFECTION OR THROMBOSIS). THE TERM STRUCTURAL VALVE DETERIORATION REFERS TO CHANGES INTRINSIC TO THE VALVE SUCH AS: WEAR, FRACTURE, CALCIFICATION, LEAFLET TEAR, MANUFACTURED SUTURE LINE DISRUPTION

"

"

"

"

"

"

"

"

"

"

"

"

"

"

"

ANY ABNORMALITY NOT INTRINSIC TO THE VALVE (DO NOT DIRECTLY INVOLVE VALVE COMPONENTS) ITSELF THAT RESULTS IN STENOSIS OR REGURGITATION OF THE OPERATED VALVE OR HEMOLYSIS (EXCLUDES THROMBOSIS AND INFECTION). EXAMPLES INCLUDE: ENTRAPMENT BY PANNUS, TISSUE, OR SUTURE, PARAVALVULAR LEAK, INAPPROPRIATE SIZING, INAPPROPRIATE POSITIONING, REGURGITATION AS A RESULT OF TECHNICAL ERROR, STJ DILATION, DILATION OF THE VALVE ANNULUS, OBSTRUCTION OF THE CORONARY OSTIA BY THE STUDY VALVE.

LEAKAGE BETWEEN THE SEWING RING AND THE ANNULUS.

"

"

"

"

NSD "

Clinical Investigational Plan

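### Read literally, AE.6 excludes emboli that coincide with any infection while AE280 takes back only those tied to study-valve infection, so some may count in neither safety endpoint

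*Combined protocol and SAP*

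**What the plan says.** Section 7.3.1 lists Thromboembolism and Endocarditis as separate safety endpoints. Section 9.3 reports each as an early percentage, a late linearized rate and a Kaplan-Meier estimate. The counting rules are in the code list of Appendix 15.1.

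- **AE.6 heading (thromboembolic event/valve thrombosis):** "ANY EMBOLIC EVENT THAT OCCURS IN THE ABSENCE OF INFECTION AFTER THE IMMEDIATE PERIOPERATIVE PERIOD".
- **AE250 (stroke) and AE255 (TIA), under that heading:** "INCLUDES ANY CENTRAL, NEW NEUROLOGIC DEFICIT, WHETHER TEMPORARY OR PERMANENT AND WHETHER FOCAL OR GLOBAL, THAT OCCURS AFTER THE SUBJECT EMERGES FROM ANESTHESIA". Both go on to list exclusions: symptoms that reproduce a documented preoperative event, events clearly due to aortic, carotid or vertebral disease, psychomotor deficits found by special testing, and patients who do not wake or who wake with a new stroke. Infection is not on the list.
- **AE256 to AE261 (other peripheral and central emboli):** the code text says nothing about infection.
- **AE262 (aortic valve thrombosis), same category:** "ANY THROMBUS NOT CAUSED BY INFECTION ATTACHED TO OR NEAR AN OPERATED VALVE".
- **AE280 (endocarditis):** "ANY INFECTION INVOLVING THE STUDY VALVE", followed by the rule that "MORBIDITIES ASSOCIATED WITH ACTIVE INFECTION, SUCH AS VALVE THROMBOSIS, THROMBOTIC EMBOLUS, BLEEDING EVENT, OR PARAVALVULAR LEAK, ARE INCLUDED UNDER THIS CATEGORY" and are not counted elsewhere.

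Sepsis (AE120), urinary infection (AE370), pneumonia (AE403) and sternal infection (AE450) have codes of their own. None of them is a safety endpoint.

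**The concern.** An exclusion of this kind works when everything it removes from one endpoint is received by another. Here the exclusion is wider than its receiver. AE.6 turns on whether an infection is present. AE280 turns on whether the study valve is infected. An embolus in a patient with an infection elsewhere can fall between the two.

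The situation is foreseeable. Section 6.2 lists wound infection, septicemia, pneumonia and thromboembolism among the risks of the operation. The trial is uncontrolled and its safety results are descriptive rates, so no comparator arm is counted under the same rule and could offset a miscount. Where the heading and the code text disagree, sites may also code like events differently. Section 11.4 asks the events committee to judge relatedness to the device and the procedure, and gives no rule for assigning an event to an endpoint.

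**Working it through.** The plan states no figure on this point, so the check is a comparison of texts, followed by the effect of one event.

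**1. Take an embolic event during a non-valve infection, with a normal study valve.**

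| Text | Test applied | Result |
|---|---|---|
| AE.6 heading | infection absent; site and cause not specified | excluded, read literally |
| AE250 / AE255 | new central deficit; infection not an exclusion | included, if a stroke or TIA |
| AE256 to AE261 | documented embolus; silent on infection | heading is the only infection rule, so excluded, read literally |
| AE280 | infection of the study valve | not met |
| AE370, AE403, AE450 | the infection itself, e.g. "LUNG INFECTION DOCUMENTED BY BLOOD STUDIES OR CHEST X-RAY" | codes the infection, not the embolus; not an endpoint |

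For the codes AE256 to AE261 the gap is plain. For stroke and TIA the two texts conflict, and the protocol does not say which prevails.

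**2. Could AE280 take the event after all?** Its sentence on active infection does not repeat the word valve, but it sits inside a category defined by study-valve infection. The diagnosis requires findings at reoperation, findings at autopsy, or the Duke criteria. An embolus during pneumonia with a normal valve meets none of these.

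**3. Is the heading operative text?** In this list, category rows carry rules. The stenosis codes in AE.5 have only ditto marks and take their definition from the row above. The exclusion of non-thrombotic emboli appears only in the AE.6 heading. The heading cannot simply be treated as a title.

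**4. Effect of one omitted event.** Inputs: up to 200 subjects (section 9.1), 5 years of follow-up (section 7), early period of 30 days (section 9.3).

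- Maximum late exposure: 200 × (5 − 30/365.25) = 983.6, about 984 subject-years.
- One late event: 1/983.6 × 100 = about 0.10 per 100 subject-years.
- If exposure were half of that (an assumption, to show the range): 1/491.8 × 100 = about 0.20 per 100 subject-years.
- One early event at N = 200: 1/200 = 0.5 percentage points.

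The documents give neither the expected number of emboli nor the share that coincide with a non-valve infection, so the total effect cannot be calculated.

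**The case against.** The strongest reply is that no event need be lost. AE250 and AE255, on their own words, count a stroke or TIA during pneumonia, and nothing says the heading overrides them. AE250 sets its own starting point, emergence from anesthesia, which differs from the heading's perioperative limit. AE262 carries its own infection test. Both suggest that code text can stand alone. Read together with AE280, the infection meant by the heading could be just the infection AE280 absorbs. The list has no neurological section, so a coder with an ischemic stroke would naturally go to AE.6. An event left out would probably still be tabulated as another complication under section 9.3. The endpoints are descriptive, and sections 9.1 to 9.3 set no threshold that a small shift could cross.

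Much of this stands. A reader might infer that a stroke during a non-valve infection definitely counts in neither endpoint, or that the thromboembolism rate is biased downward by a known proportion. The documents support neither. The first requires the heading to override AE250 and AE255, which is not stated. The second needs a share of affected events that is not given, and if the stroke and TIA codes govern, the loss for those events is zero.

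The reply does not remove the problem. It leaves AE256 to AE261 with the heading as their only infection rule. For stroke and TIA it replaces a lost event with an unresolved conflict. Tabulation as another complication keeps the event visible but outside the named endpoint.

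**Conclusion.** The wording is defective as it stands. Followed literally, AE.6 excludes more than AE280 receives, so an embolic event during a non-valve infection may be missing from both endpoints. For stroke and TIA the same event can be classified either way. A downward bias follows only if the heading governs; otherwise the harm is inconsistent coding.

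The number of such events is unknown and probably small. The per-event effects in the working assume 200 subjects and, for the late rate, complete 5-year follow-up; with less exposure or fewer subjects each event weighs more. No stated decision rule depends on the result. The case for acting is that this is a counting rule for a named safety endpoint and the correction costs very little.

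**What to change.** In the AE.6 heading, replace the clause requiring the absence of infection with: *EXCEPT EVENTS COUNTED UNDER AE280 (ENDOCARDITIS)*. Keep the timing limit and the rest of the sentence. Defining the exclusion by what AE280 counts makes the two categories fit exactly. A causal phrase limited to valve infection would not, because AE280 takes emboli associated with active infection, and an embolus during but not caused by endocarditis would then meet both definitions.

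State in Appendix 15.1 that the category heading and the code definitions apply together. This also applies the heading's perioperative limit to AE250 and AE255, so the sponsor should confirm that this is intended.

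Check whether any embolic event was coded outside AE.6 solely because a non-valve infection was present.

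The cost is one clause and one sentence in an appendix that section 15 allows to be updated independently, plus a review of coded events. The downside is that the reported thromboembolism rate may rise slightly.

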7.3 ENDPOINTS

7.3.1 SAFETY ENDPOINTS

Descriptive information of early rates and late linearized rates of the following:

- Structural valve deterioration
- Thromboembolism
- All bleeding/hemorrhage
- Major bleeding/hemorrhage
- All paravalvular leak
- Major paravalvular leak
- Non-structural valve dysfunction
- Endocarditis
- Hemolysis
- All cause mortality
- Trial valve-related mortality
- Explant

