11.4 CLINICAL EVENTS COMMITTEE

The Clinical Events Committee (CEC) evaluates adverse events that are endpoint related. The CEC adjudicates events for their relatedness to the investigational device and/or the surgical procedure. The CEC will be composed of physicians familiar with the treatment of valvular heart disease and cardiac surgery who are not participating in the investigational trial.

The trial Sponsor will provide the CEC completed case report forms and any relevant source documentation/subject information as provided by the clinical site investigators. Trial Sponsor will insure that all information is de-identified before presenting to the committee. The CEC documents its findings or rulings on each event. All meeting minutes and supporting documentation are maintained by the CEC administrator with a copy provided to the trial Sponsor.

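### Non-infective thrombosis of the study valve is shut out of both valve-dysfunction endpoints and is not an endpoint itself, so it has no planned Kaplan-Meier rate and no assured committee adjudication

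*Combined protocol and SAP*

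**What the plan says.** Section 7.3.1 and the synopsis introduce the safety endpoints as "Descriptive information of early rates and late linearized rates of the following" and list 12 items. Structural valve deterioration, non-structural valve dysfunction, thromboembolism, endocarditis, trial valve-related mortality and explant are among them. Valve thrombosis is not.

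Appendix 15.1 defines the two dysfunction endpoints in group AE.15. The structural definition "INCLUDES DYSFUNCTION OR DETERIORATION INVOLVING THE OPERATED VALVE (EXCLUSIVE OF INFECTION OR THROMBOSIS"). The non-structural definition covers an abnormality not intrinsic to the valve that "RESULTS IN STENOSIS OR REGURGITATION OF THE OPERATED VALVE OR HEMOLYSIS (EXCLUDES THROMBOSIS AND INFECTION").

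Valve thrombosis sits in group AE.6, headed "CARDIOVASCULAR - THROMBOEMBOLIC EVENT/VALVE THROMBOSIS". The lead definition of that group is "ANY EMBOLIC EVENT THAT OCCURS IN THE ABSENCE OF INFECTION AFTER THE IMMEDIATE PERIOPERATIVE PERIOD". AE262, labelled "VALVE THROMBOSIS - AORTIC", then has its own definition: "ANY THROMBUS NOT CAUSED BY INFECTION ATTACHED TO OR NEAR AN OPERATED VALVE THAT OCCLUDES PART OF THE BLOOD FLOW PATH", or that interferes with valve function, or that is large enough to need treatment. Thrombus found incidentally at autopsy or at an unrelated operation is also to be counted.

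Section 9.3 plans Kaplan-Meier rates for the safety endpoints. All remaining complications get early percentages and late linearized rates. Section 11.4 states: "The Clinical Events Committee (CEC) evaluates adverse events that are endpoint related".

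**The concern.** The two dysfunction definitions remove two causes of valve malfunction, infection and thrombosis, in the same words. Infection is picked up again by a listed endpoint, endocarditis. Thrombosis is picked up by none that clearly fits. The plan thus recognises a device-specific way for the valve to malfunction, defines it carefully, and then leaves it outside the set of events that receive the full analysis.

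Two things are at stake. First, whether a thrombus is on the study valve, and whether it is related to the device, is a judgement that benefits from independent adjudication, and section 11.4 does not assure it for this event. Second, the thromboembolism endpoint is open to two readings. One analyst could count AE262 in it because the code group and the case report form class are shared. Another could leave it out because the definition is embolic. The same data would then give different thromboembolism rates whenever an AE262 event occurs.

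**Working it through.** No arithmetic applies. The plan states no rate, margin or expected count for valve thrombosis. The check is to follow an AE262 event through each place where it could be counted.

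1. **Structural valve deterioration (7.3.1; AE.15).** Excludes thrombosis. Not counted.
2. **Non-structural valve dysfunction (7.3.1; AE.15).** Excludes thrombosis. Not counted. So 2 of 2 dysfunction definitions exclude it.
3. **Regurgitation and stenosis codes (AE.3, AE.5).** When the study valve is involved, the code list tells sites to report the event as structural or non-structural dysfunction. If thrombus is the cause, both destinations exclude it, so this route leads back to steps 1 and 2.
4. **Endocarditis (7.3.1; AE280).** Valve thrombosis associated with active infection is counted here and nowhere else. AE262 covers thrombus not caused by infection. The gap therefore concerns non-infective thrombosis.
5. **Thromboembolism (7.3.1; AE.6).** The group heading names two event types side by side, and the group's lead definition requires an embolic event. A thrombus that stays on the valve does not meet it. The Assessment, Surgery Data and Adverse Event forms in Appendix 15.3 nevertheless offer embolic events and valve thrombosis as one class. No section says whether AE262 feeds the endpoint.
6. **Explant, valve-related mortality, all-cause mortality (7.3.1).** A thrombosis that leads to one of these is counted there by its consequence, not its cause. For an incidental finding at autopsy after a death that was not valve related, the death enters all-cause mortality but the thrombus enters no endpoint.
7. **Named endpoint.** 0 of 12.

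What remains is a non-infective thrombus that is treated or found without embolism, explant or valve-related death. Reading the embolic definition literally, the plan gives it:

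| Output | Listed endpoint | AE262 as written |
|---|---|---|
| Early percentage (9.3) | yes | yes, as an other complication |
| Late linearized rate (9.3) | yes | yes, as an other complication |
| Kaplan-Meier rate at each follow-up point (9.3) | yes | not planned |
| CEC evaluation (11.4) | yes | not assured |

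If AE262 is instead folded into thromboembolism, it gets Kaplan-Meier reporting and CEC review, but only pooled with strokes, transient ischaemic attacks and peripheral emboli, and with no endpoint rate of its own. Neither reading gives valve thrombosis its own actuarial rate.

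**The case against.** The strongest reply is that little is missing. AE262 is coded, defined and collected, and section 9.3 gives it the early and linearized rates that section 7.3.1 promises for endpoints. With few events, a Kaplan-Meier curve adds modestly to a linearized rate. The study is observational and non-controlled, with no hypothesis or success criterion in section 9, so no decision rule turns on this. Thrombus is also looked for independently: the Echo Core Lab results form records it under aortic valve morphology. A single sentence mapping AE262 would remove the ambiguity.

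Much of this stands, and it rules out some stronger readings that a reader might infer:

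- *That valve thrombosis goes unreported.* It does not; section 9.3 covers it.
- *That the CEC is barred from seeing it.* Section 11.4 describes what the committee evaluates without limiting it to listed endpoints, and endpoint-related is wider than endpoint. The supportable statement is that review is not assured.
- *That the endpoint list claims to cover every way the valve can fail.* No section says so. The stated purpose in section 7.2 is to gather further data confirming safety and performance.

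What does not stand is the suggestion that a mapping sentence alone is enough. If it sends AE262 to thromboembolism, the event is pooled with emboli and the endpoint departs from its own definition. If it keeps AE262 out, the actuarial rate and assured adjudication are still missing. The core lab reading depends on an echocardiogram being done, and at years 2 and 4 that happens only if a murmur is heard. It also does not adjudicate relatedness.

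**Conclusion.** The point holds in a limited form. Non-infective thrombosis of the study valve is a recognised device risk that both dysfunction endpoints exclude and no endpoint names. As written it lacks a planned Kaplan-Meier rate and assured CEC adjudication unless it leads to a listed endpoint, and its relation to the thromboembolism endpoint is unstated.

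The size is one event type, one of three planned summaries, and the adjudication step. A reader might want to express this as a percentage by which valve failure is understated. The documents do not support such a figure: they give no thrombosis rate and no expected dysfunction count, and the plan never calculates a total of valve failures. The endpoint list is not built to be summed, since major leak is a subset of all leak and paravalvular leak is itself an example of non-structural dysfunction. The structural and non-structural rates would be correct under their own definitions.

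The conclusion rests on reading the AE.6 lead definition as governing the thromboembolism endpoint. On the other reading, AE262 is analysed and adjudicated but cannot be seen separately. The change is worth making on either reading.

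**What to change.** Add valve thrombosis (AE262, study valve) as a separate line in section 7.3.1 and in the synopsis. It then falls under the early, linearized and Kaplan-Meier reporting of section 9.3 and the CEC remit of section 11.4 without further edits there. State in section 9.3 or Appendix 15.1 that the thromboembolism endpoint does not include AE262. An embolus arising from a valve thrombus would still be counted as thromboembolism under its own AE.6 code, and infected thrombosis would stay under endocarditis as now defined.

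The cost is one more row in the endpoint tables and a few more CEC reviews. The code and definition already exist, and thrombus is already recorded on the core lab and explant forms. No new data are needed, provided that events are coded to the individual AE numbers and not only to the combined class on the forms.
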